4.3.5 Duration of Intervention and Follow-up Period

It is anticipated that participants who are randomized early will be followed for approximately 4 years for development of the primary outcome, diabetes. Because D2d is an event-driven trial, follow up periods are estimates and will depend on rates of enrollment and retention. There are no definitive data to determine the optimum duration of exposure to vitamin D required to affect diabetes risk. In an observational study in the Nurses' Health Study, women with the highest 25OHD concentration at baseline had a reduction in diabetes by 40% over an approximate 10-year follow-up period.²² In the Framingham Offspring Study, participants in the highest tertile of predicted 25OHD score had a 40% lower incidence of diabetes during a 6-year follow-up period.²¹ Of particular relevance to the D2d trial, in the Diabetes Prevention Program (DPP) cohort, participants with pre-diabetes who had a plasma 25OHD concentration ≥ 30 ng/mL at baseline had a 28% risk reduction in incident diabetes over a 3-year period, after adjustment for the DPP lifestyle intervention.²⁵ In the Stockholm Diabetes Prevention Program, among participants with pre-diabetes, the risk of progression to type 2 diabetes was reduced by 62% among those with blood 25OHD above 28 ng/mL compared to those with 25OHD lower than 18 ng/mL over a 8-year follow-up, which corresponds to a 23% reduction for each 4 ng/mL increase in blood 25OHD concentration.¹⁹⁵ These results are consistent with other observational cohorts.²⁶⁻²⁸ A post-hoc analysis of a completed trial showed a reduction of approximately 90% in FPG and insulin resistance (HOMA-IR) in participants with pre-diabetes after 3 years of supplementation with vitamin D.¹⁹ In the RECORD trial, a trend towards reduced diabetes risk was seen with vitamin D supplementation after 2-4 years of follow up.¹⁴⁸ In the CaDDM trial, among participants with pre-diabetes, 2,000 IU/day of vitamin D₃ improved measures of beta cell function (disposition index) by approximately 40% and glycemia (HbA1c) by approximately 50% after 4 months.²⁴ In addition to vitamin D-specific mechanisms, the planning committee also took into consideration additional issues, including practical ones, when deciding on the follow-up period, as follows: (1) a shorter follow-up period will minimize "study fatigue" by study personnel and participants, and will maximize retention; (2) a shorter follow-up period will allow the study to be

completed faster and results disseminated to the scientific community and public earlier, although with a shorter follow-up period, more participants need to be recruited, to ensure sufficient statistical power; (3) adequate follow-up is required to allow progression to diabetes to occur; (4) supplementation is expected to achieve steady state level of plasma 25OHD concentration within 4 months in the majority of participants;^{24,229-231} (4) the rate of progression from pre-diabetes to diabetes is expected to be about 10% per year in the control arm, which is a rate high enough to allow for a statistical comparison with the active arm. After considering all these issues, an average follow up period of approximately 3 years is expected, with early enrollees being followed for approximately 4 years and the sample size was calculated accordingly.

Rationale for lack of run-in period. A run-in period before randomization could identify participants whose 25OHD concentration may not respond to vitamin D or develop side effects and also could identify participants that are likely to become low adherers, thereby increasing adherence to study medications and retention. However, a run-in period was not included in the study design because it would add considerable expense without proportional benefit as the proposed intervention and assessment of outcomes are relatively low-burden and vitamin D supplementation raises 25OHD concentration in all participants (although the degree of rise may vary). Furthermore, external validity may be lessened in studies that include a run-in period.²³²

4.3.6 Advice on Lifestyle

Eligible participants are at increased risk for diabetes. In accordance with the latest ADA Standards of Care,²³³ at baseline, the study will: (1) provide enrolled participants with written information on the current recommendations for prevention of type 2 diabetes, which emphasizes lifestyle intervention aiming to achieve and maintain at least a 5% weight loss and increased physical activity to at least 150 min/week of moderate activity;²³³ (2) send a letter to participants' primary care providers indicating that participants are at risk for diabetes and to advocate efforts at weight loss and increasing physical activity. This approach is consistent with the lifestyle advice that was provided to participants in other type 2 diabetes prevention trials that have compared medications with placebo.^{11-13,16} Importantly, during the study, all participants will be invited to join the D2d Support and Education Program (SEP). As part of this program, participants will attend group meetings, held twice yearly at each site, to discuss specific topics in nutrition, exercise and diabetes (e.g. healthy eating strategies for the holidays). These meetings will allow the opportunity to meet other participants and will also serve as a way to enhance retention. The Recruitment and Retention subcommittee will suggest topics that the sites can utilize for these meetings. Finally, participants will receive a D2d study newsletter at regular intervals, which will include a section on healthy nutrition and exercise. Participants may lose some weight during the study, but this is not expected to confound the results as it is anticipated that weight change will be similar between arms.

4.3.7 Measurements of Other Exposures

Vitamin D status. Plasma 25OHD concentration will be measured as a proxy for vitamin D status at baseline and yearly during follow-up to assess the efficacy of the intervention in the active arm at improving vitamin D status and to evaluate for heterogeneity of treatment effect by achieved 25OHD concentration. Measurement of 25OHD will not be done in real-time (see 7.6). *Self-reported vitamin D intake* will be estimated from a validated self-administered semi-quantitative food frequency questionnaire administered at baseline, month 12 and month 36 in participants free of diabetes.^{18,234-237}

Calcium status. There are no widely accepted measures of adequacy of calcium status. Calcium intake will be used as proxy of calcium adequacy at baseline and during the intervention. *Self-reported calcium intake* will be estimated from a validated food frequency questionnaire administered at baseline, month 12 and month 36 in participants free of diabetes.¹⁸

4.3.8 Principles Guiding Selection of Patient Population

Rationale for selection of a population with pre-diabetes. The study will recruit and follow participants with pre-diabetes. The target population was selected based on published data from post-hoc analyses of a completed trial designed for skeletal outcomes,¹⁹ which showed that vitamin D supplementation had a favorable effect on FPG and insulin resistance (HOMA-IR) only among participants with pre-diabetes at baseline. These findings were confirmed by results from the CaDDM trial among participants with pre-diabetes, which showed that oral vitamin D₃ supplementation (2,000 IU/day) improved the disposition index (a measure of beta cell function that accounts for the prevailing insulin sensitivity) and glycemia.²⁴ In contrast, other studies (most were underpowered) did not report an effect of vitamin D supplementation on glycemia among those with normal glucose tolerance or established diabetes.^{32,33,45,47,166} Therefore, D2d is focused on a population with pre-diabetes, which would be the most likely group to benefit from the proposed intervention.

The ADA guidelines define that a pre-diabetes state (“at increased risk for diabetes”) exists when a patient does not meet criteria for diabetes and meets one of the following criteria: FPG 100-125 mg/dL **or** 2hPG 140-199 mg/dL **or** HbA1c 5.7-6.4%.²³³ The addition of HbA1c as a criterion for the diagnosis of pre-diabetes is expected to increase the number of patients diagnosed with pre-diabetes but may also identify patients at different risk compared to the definition using only the FPG or 2hPG criteria. *For the D2d trial, pre-diabetes is defined if 2-out-of-3 ADA glycemic criteria for pre-diabetes are met.* This definition was chosen to identify a population that is at somewhat higher risk for developing diabetes than when diabetes is defined by only 1-out-of-3 criteria. As a result, the D2d target population will: (1) potentially benefit the most from the proposed intervention and (2) have a higher conversion rate to clinical diabetes, thereby lowering the required sample size.

Rationale for chosen age range. The study will include participants equal to or older than 30 years (≥25 years for people of the following high-risk races: American-Indian, Alaska Native, Native Hawaiian or Other Pacific Islander). Risk for pre-diabetes increases with age but we chose a lower age than what is typically considered higher risk (>45 years), because lower age at diagnosis of pre-diabetes is associated with higher progression to diabetes.⁵ Also, this age cutoff would reduce “contamination” with type 1 diabetes or Latent Autoimmune Diabetes of Adults and minimize loss to follow-up due to social mobility. The planning committee selected no upper age limit to increase the generalizability of findings and to allow for heterogeneity of treatment effect (subgroup) analyses by age.

Rationale for chosen weight/body mass index range. The study will include participants with a BMI equal to or higher than 24 (22.5 kg/m² for Asians) but not higher than 42 kg/m² because overweight/obesity is a significant risk factor for type 2 diabetes and because those with severe obesity require much higher doses of vitamin D to achieve the desired 25OHD concentration.²³⁸

Rationale for lack of “low vitamin D status” as an inclusion criterion: Vitamin D status (assessed by blood 25OHD concentration) at baseline is not an inclusion criterion for the following reasons: (1) in small trials, vitamin D benefited those with pre-diabetes irrespective of baseline 25OHD concentration;^{19,24} (2) the definition of ‘optimal’ vitamin D status is controversial and no consensus exists on optimal blood 25OHD level,^{172,176,185,239-243} (3) suboptimal vitamin D status is widespread in the U.S. adult population, especially among overweight and obese persons,^{49,198,244-250} (4) to ensure that the study is as “pragmatic” as possible and results are generalizable to clinical practice,²⁵¹ (5) baseline 25OHD is a treatment selection marker to enter the heterogeneity of treatment effect (subgroup) analyses and to assess its performance, participants with a wide range of 25OHD must be enrolled;²⁵² (6) 25OHD concentration varies by season,^{185,253} and may decrease during acute phase response,^{254,255} (7) screening with 25OHD would be cumbersome and expensive. All participants will be encouraged to take the IOM recommended dose of vitamin D for their age.

Other clinical characteristics: Study participants with pre-diabetes will have baseline clinical characteristics (age, gender, race, ethnicity, BMI) representative of the U.S. adult population with pre-diabetes. The target cohort will aim to include a large number of minorities (30-40%, including Black or African American, American Indian/Alaska Native, Asian, Native Hawaiian/Pacific Islander, Hispanic) and women (50%). Participating clinical sites, where recruitment will take place, are selected to ensure adequate distribution of these characteristics in the cohort.

Potential Differences by Race and Ethnic Composition – In the preliminary studies, there was no difference among whites vs. non-whites in the association between 25OHD and incident diabetes in the DPP²⁵ or with vitamin D supplementation (CaDDM trial).²⁴ Nevertheless, given that non-whites have higher risk of t2DM and different vitamin D-calcium homeostasis, D2d aims to recruit a large proportion, of *non-whites and analyses will test for heterogeneity of treatment effect by race and ethnicity. Race or ethnicity appear to be better determinants of 25OHD variability than objective measures of skin color*¹⁸⁶ suggesting that behavioral variables or physiological variables, other than biosynthesis, may be important in determining 25OHD concentration. Therefore, D2d has not incorporated objective measures of skin color in the study design, because these methods are labor-intensive and difficult to standardize among sites. Data on race and ethnicity data are collected by participant self-report.

5. STUDY POPULATION

Specific participation (inclusion/exclusion) criteria are described below. A brief justification for each inclusion/exclusion criterion, if necessary, is shown in brackets [...]

5.1 Inclusion Criteria

1. Pre-diabetes (“at increased risk for diabetes”) defined by meeting 2-out-of-3 of the following glycemic criteria, established by the ADA in the 2010 clinical practice guidelines, at the baseline visit.²³³
 - a. FPG 100-125 mg/dL, inclusive
 - b. 2hPG 140-199 mg/dL, inclusive
 - c. HbA1c 5.7-6.4%, inclusive
2. Age \geq 30 years, (\geq 25 years for people of the following races: American-Indian, Alaska Native, Native Hawaiian or Other Pacific Islander). [Age is a major risk factor for type 2 diabetes; avoid “contamination” with type 1 Diabetes or Latent Autoimmune Diabetes of Adults, conditions that have a different pathophysiology; minimize loss to follow-up due to social mobility; facilitate recruitment and increase applicability of findings; onset of type 2 diabetes is earlier in the certain high-risk ethnic groups]
3. BMI \geq 24.0 (22.5 for Asians) and \leq 42.0 kg/m.² [Overweight/obesity is a major risk factor for type 2 diabetes; those with severe obesity require higher doses of vitamin D²³⁸]
4. Provision of signed and dated written informed consent prior to any study procedures.

5.2 Exclusion Criteria

Exclusion Criteria were selected to: (1) ensure participants’ safety; (2) avoid conditions that would affect the outcomes (i.e. minimize competing risk); (3) make recruitment targets realistic; (4) amplify generalizability of study results; (5) maximize participants’ adherence with study procedures.

5. Diabetes based on *either* of the following criteria:
 - a. History (past 1 year) of hypoglycemic pharmacotherapy (oral or injectable medication approved by the FDA for type 2 diabetes) used for any condition (e.g. pre-diabetes, diabetes, polycystic ovarian syndrome).
 - b. Meeting a glycemic criterion for diabetes, as defined by the ADA guidelines (FPG \geq 126 mg/dL, 2hPG \geq 200 mg/dL or HbA1c \geq 6.5%) at the baseline visit.
6. History (past 3 years) of hyperparathyroidism, symptomatic or asymptomatic (i.e., radiographic) nephrolithiasis or hypercalcemia. [Safety]
7. Any medical condition (past 3 years) that in the opinion of the site investigator may increase risk for nephrolithiasis or hypercalcemia during the trial (e.g. sarcoidosis). [Safety]
8. Use of tanning devices within 12 weeks of the baseline visit and unwilling to stop using tanning devices for the duration of the study [interference with intervention]

Medications and Supplements

9. Use of supplements containing vitamin D at total doses higher than 1000 IU/day within 8-12 weeks (depending on dose, as described in Manual of Operations) of the baseline visit initiating the protocol and unwillingness to limit vitamin D supplementation dosage to no higher than 1000 IU/day for the duration of the study. [Safety]
10. Use of supplements containing calcium at total doses higher than 600 mg/day within 1 week of the baseline visit initiating the protocol and unwillingness to limit calcium supplementation dosage to no more than 600 mg/day for the duration of the study. [Safety]
11. Current use of medications or conditions (e.g. untreated celiac disease) that would interfere with absorption or metabolism of vitamin D.

12. Current use of medications approved by the FDA for weight management.
13. Use of thiazide diuretics at a total dose greater than 37.5 mg/day.
14. Use of anticonvulsant drug started within 6 months of screening. Stable regimen of anticonvulsants is allowed.
15. History of intolerance to vitamin D supplements. [Safety]

Other Medical History

16. Severe symptomatic cardiovascular disease based on history and physical examination (unstable angina, dyspnea on exertion, paroxysmal nocturnal dyspnea, arrhythmia, congestive heart failure NYHA class II or higher, claudication).
17. History (past 1 year) of myocardial infarction, percutaneous coronary intervention or coronary artery bypass graft. [Safety]
18. History (past 1 year) of cerebrovascular disease (stroke, transient ischemic attack). [Safety]
19. Any type of cancer (past 5 years) except for basal cell skin cancer. [Safety] Participants with prostate cancer (for men over age 55) or well-differentiated thyroid cancer that are not expected to require treatment (except for suppression with thyroid hormone) over the next 4 years are *not excluded*. Volunteers with history of squamous cell cancer of the skin, which was completely excised and with no evidence of metastases, are eligible.
20. History (past 6 months) of treatment with oral (for > 7 days) or intravenous glucocorticoids or disease likely to require oral or intravenous glucocorticoid therapy during the study). [Interference with outcome assessment] Inhaled glucocorticoid use is not an exclusion. Epidural or intra-articular glucocorticoid injections are not exclusions but study visits need to be conducted at least a week after the injection. Persons with adrenal insufficiency treated with physiologic doses of glucocorticoids who are otherwise stable are *not excluded*.
21. History (past 1 year) of substance abuse or unstable psychiatric disorder that in the opinion of the site investigator would impede competence or adherence with study procedures or hinder completion of the study or increase risk. [Safety, adherence] Use of marijuana with a medical prescription is permitted.
22. History of bariatric surgery (e.g., Roux-en-Y gastric bypass, gastric sleeve) or planned bariatric surgery in the next 4 years. Participants with gastric banding more than 2 years ago with self-reported weight stability (defined as weight change no greater than 3 kg during the prior 6 months) are *not excluded*. [Interfere with vitamin D absorption]
23. A life-threatening event within 30 days of screening or currently planned major surgery.
24. Any other unstable active medical condition (including but not limited to liver disease, wasting illness, AIDS, tuberculosis, oxygen-dependent chronic obstructive pulmonary disease, organ transplant, Cushing's syndrome) that in the opinion of the site investigators would impede competence or adherence with study procedures or increase risk. [Safety, adherence, plasma 25OHD may decrease as an acute-phase response^{254,255}] Such conditions will be assessed based on self-report and/or review of medical records (if available).
25. Uncontrolled hypertension (systolic blood pressure > 160 mm Hg or diastolic blood pressure > 100 mm Hg). [Safety]
26. Poor venous access. [Safety]

Laboratory Evaluation

27. Serum liver transaminase (ALT or AST) higher than 3 times the normal range for the clinical site's laboratory [Safety]
28. Anemia (hematocrit < 32 for women, < 36 for men), whole blood transfusion (within 6 months of screening) or chronic requirement, whole blood donation (within 3 months of screening) or other condition (hemolysis, hemoglobinopathy) rendering HbA1c results unreliable as indicator of chronic glycemia. [Interference with outcome assessment] Participants who donate platelets are

not excluded. Whole blood transfusion or donation does *not* exclude participant, but screening and study visits need to be timed appropriately.

29. Low platelet count (< 50,000). [Safety for blood draws]
30. Chronic kidney disease, defined as estimated glomerular filtration rate [GFR] < 50 mL/min, from creatinine measured at the clinical site's laboratory and GFR calculated centrally. [Vitamin D homeostasis changes as GFR declines. These changes start when GFR falls around 40-60 mL/min per 1.73 m².^{256,257} The planning committee selected 50 mL/min as the exclusion cutoff to ensure that participants maintain GFR > 40 mL/min during the study] Please note: to prevent potential confusion, GFR units will be denoted as mL/min throughout the protocol and associated documents.
31. Hypercalcemia, defined as serum calcium concentration greater than or equal to the upper limit of normal, measured at the clinical site's laboratory. [Safety]
32. Hypercalciuria, defined as spot urine (morning void) calcium-creatinine ratio > 0.275.²⁵⁸ [Safety]

Other

33. Participation (within 30 days of screening) in another interventional research study. [Conflict, "contamination"]
34. Previous randomization in the D2d study. Participants who did not qualify after screening may be screened again if the prior reason for exclusion has been addressed (e.g. high blood pressure is treated).
35. Any other reason that in the opinion of the site investigator would impede adherence with study procedures or hinder completion of the study or increase risk (e.g. use of non-approved or experimental drugs, inability to follow instructions or understand the informed consent, dementia, unable to remain in the program for the duration of the study, inability to comply with the study protocol for any reason). [Safety, adherence]

Women only

36. Pregnancy (past 1 year by report or positive pregnancy test at screening), intent to become pregnant in the next 4 years or unprotected intercourse. [Safety] History of gestational diabetes is *not* an exclusion criterion.
37. Currently breastfeeding. [Safety]
38. Use of oral contraceptives or menopausal hormone therapy started within 3 months of baseline. Stable regimen of oral contraceptives or any other hormonal method of contraception (e.g. implantable) is allowed. [Safety, interference with intervention]

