	
5. Diabetes based on either of the following criteria:
a. History (past 1 year) of hypoglycemic pharmacotherapy (oral or injectable medication approved by the FDA for type 2 diabetes) used for any condition (e.g. pre-diabetes, diabetes, polycystic ovarian syndrome).b. Meeting a glycemic criterion for diabetes, as defined by the ADA guidelines (FPG ≥ 126 mg/dL, 2hPG ≥ 200 mg/dL or HbA1c ≥ 6.5%) at the baseline visit.6. History (past 3 years) of hyperparathyroidism, symptomatic or asymptomatic (i.e. radiographic) nephrolithiasis or hypercalcemia.

7. Any medical condition (past 3 years) that in the opinion of the site investigator may increase risk for nephrolithiasis or hypercalcemia during the trial (e.g., sarcoidosis).
8. Use of tanning devices within 12 weeks of the baseline visit and unwilling to stop use of tanning devices for the duration of the study

Medications and Supplements

9. Use of supplements containing vitamin D at total doses higher than 1000 IU/day within 8-12 weeks (depending on dose, as described in the Manual of Operations) of the baseline visit and unwillingness to limit vitamin D supplementation dosage to no higher than 1000 IU/day for the duration of the study.
10. Use of supplements containing calcium at total doses higher than 600 mg/day within 1 week of the baseline visit and unwillingness to limit calcium supplementation dosage to no more than 600 mg/day for the duration of the study.
11. Current use of medications or conditions (e.g. untreated celiac disease) that would interfere with absorption or metabolism of vitamin D.
12. Current use of medications approved by the Food and Drug Administration (FDA) for weight management.
13. Use of thiazide diuretics at a total dose greater than 37.5 mg/day.
14. Use of anticonvulsant drug started within 6 months of screening. Stable regimen of anticonvulsants is allowed.
15. History of intolerance to vitamin D supplements.

Other Medical History

16. Severe symptomatic cardiovascular disease based on history and physical examination (unstable angina, dyspnea on exertion, paroxysmal nocturnal dyspnea, arrhythmia, congestive heart failure NYHA class II or higher, claudication)
17. History (past 1 year) of myocardial infarction, percutaneous coronary intervention or coronary artery bypass graft.
18. History (past 1 year) of cerebrovascular disease (stroke, transient ischemic attack).

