4.3.4 Case for Permitting Supplements Outside of the Study

Based on NHANES data, the average intake of vitamin D in the D2d target age group was approximately 400 IU/day, including from diet and supplements. The study will encourage all participants to optimize their dietary vitamin D intake and supplement their intake of vitamin D from supplements up to 600 or 800 IU per day (depending on their age); however, participants will be discouraged from taking vitamin D-containing supplements on their own throughout the trial, *beyond what is recommended by the Institute of Medicine for their age group (600 or 800 IU/day)*, unless specifically prescribed by a physician. The planning committee recognized that for practical reasons, participants may take up to 1000 IU/day of vitamin D on their own from all supplemental sources combined (stand-alone vitamin D supplements, multivitamins, medications containing vitamin D [e.g. Fosamax Plus D]), if they wish. The maximum allowable dose of 1000 IU/day was chosen because it is the dosage contained in many commercially available supplements and also commonly recommended by health care providers. Participants who are unwilling to limit outside-of-study vitamin D intake from supplements to 1000 IU/day for the duration of the study will be excluded from participating. During screening, potential participants who are taking more than the allowed vitamin D dose from supplements will be excluded from the study, unless they agree to lower their supplemental intake to no more than 1000 IU/day for 8-12 weeks (depending on dose) prior to initiating the protocol and also agree not to exceed this supplemental threshold during the entire study.

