Calcium Supplements: The Institute of Medicine recommendation for total (dietary and supplemental) calcium intake for adults is 1000-1200 mg/day from either food or supplements; however, there is concern that high calcium intakes from supplements may be associated with adverse cardiovascular effects and development of nephrolithiasis. The current recommendation is to optimize calcium intake through diet with supplementation only as needed to reach the recommended total intake. In the CaDDM trial, among persons with pre-diabetes – a population identical to D2d – total calcium intake was 976 mg per day, nearly all of it coming from dietary sources (859 mg per day), which is consistent with calcium intake in the general population.^{18,185,224-226} Therefore, participants will not be allowed to take more than 600 mg/day of calcium on their own from all supplemental sources combined (e.g. stand-alone calcium supplements, multivitamins, medications containing calcium [e.g. Actonel with Calcium]), unless specifically prescribed by a physician. Participants who are unwilling to limit calcium supplementation to 600 mg/day for the duration of the study will be excluded from participating. During the pre-screening, potential participants who are reporting more than the allowed calcium intake from supplements will be excluded from the study, unless they agree to lower their supplemental intake to no more than 600 mg/day or less for 1 week prior to the screening visit and also agree not to exceed this supplemental threshold during the study.

Other supplements: Participants are free to take additional vitamins or supplements that do not contain vitamin D or calcium on their own. All supplement use (with or without vitamin D) will be recorded, based on self-report, at each visit.

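### Exclusion criteria 9 and 10 require both recent above-limit supplement use and unwillingness to limit it, whereas section 4.3.4 makes either one sufficient to exclude

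*Protocol*

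**What the plan says.** Criteria 9 (vitamin D) and 10 (calcium) appear twice in the Protocol, in section 5.2 and in the synopsis.

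- **5.2, criterion 9:** supplemental vitamin D above 1000 IU/day within 8-12 weeks (dose-dependent, with a reference to the Manual of Operations) "of the baseline visit initiating the protocol and unwillingness to limit vitamin D supplementation dosage to no higher than 1000 IU/day".
- **5.2, criterion 10:** supplemental calcium above 600 mg/day "within 1 week of the baseline visit initiating the protocol and unwillingness to limit calcium supplementation dosage to no more than 600 mg/day".
- **Synopsis, criterion 9:** the same join, "of the baseline visit and unwillingness to limit vitamin D supplementation dosage to no higher than 1000 IU/day for the duration of the study".
- **Synopsis, criterion 10:** the same join, "Use of supplements containing calcium at total doses higher than 600 mg/day within 1 week of the baseline visit and unwillingness to limit".

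In 5.2 both criteria are tagged as safety criteria. Under section 6.5 a volunteer goes on to the baseline visit only if no exclusion criterion applies.

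Section 4.3.4 gives two separate rules for each supplement.

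- **Unwillingness alone.** For vitamin D, people "unwilling to limit outside-of-study vitamin D intake from supplements to 1000 IU/day for the duration of the study will be excluded from participating". For calcium, "Participants who are unwilling to limit calcium supplementation to 600 mg/day for the duration of the study will be excluded from participating".
- **Washout.** Current above-limit vitamin D users are excluded "unless they agree to lower their supplemental intake to no more than 1000 IU/day for 8-12 weeks" before the protocol starts, and they must also accept the limit for the whole study. Above-limit calcium users must come down to "no more than 600 mg/day or less for 1 week prior to the screening visit", and must likewise accept the limit during the study.

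**The concern.** An exclusion criterion that joins two conditions with *and* applies only when both are true. Section 4.3.4 describes two conditions, each of which is enough. The criteria list is what a site applies at screening, and as written it is weaker than the rule the protocol explains elsewhere.

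What is at stake is mainly safety at entry. The trial gives 4,000 IU/day, which section 4.3.1.2 identifies as the Institute of Medicine's tolerable upper intake level, and section 10.1.1 lists hypercalcemia and nephrolithiasis among the expected risks. The washout keeps volunteers from starting study pills on top of recent high-dose supplements. A smaller matter is that baseline 25OHD (below 20 versus 20 ng/mL or more) defines a subgroup in SAP 4.3.1, so a volunteer who has had no washout could be classified on a value that reflects the earlier supplement.

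**Working it through.** The plan gives no figure to reproduce on this point; the check is one of logic.

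**Inputs.** Let U mean above-limit use inside the washout window, and W mean unwillingness to keep to the limit during the study. For this step, take the window as the same in both places; the calcium anchor is treated separately below.

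- Criteria 9 and 10 as written (5.2 and synopsis): exclude if U *and* W.
- Section 4.3.4: exclude if W (the unwillingness sentences); exclude if U, because the washout has not been done. Together: exclude if U *or* W.

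| U (recent above-limit use) | W (unwilling) | Criteria 9/10 as written | Section 4.3.4 | Agree? |
|---|---|---|---|---|
| no | no | admit | admit | yes |
| no | yes | admit | exclude | **no** |
| yes | no | admit | exclude | **no** |
| yes | yes | exclude | exclude | yes |

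Two of the four combinations disagree, in the same way for both supplements.

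**Willing recent user, no washout (U yes, W no).** Section 4.3.4 requires 8-12 weeks (vitamin D) or 1 week (calcium) at or below the limit first. Criteria 9 and 10 ask for nothing once the volunteer agrees to the limit from now on. No other criterion clearly catches this person.

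**Unwilling volunteer, no recent above-limit use (U no, W yes).** Section 4.3.4 excludes; criteria 9 and 10 do not. There is a partial backstop: section 9.4 caps supplements on study at 1000 IU and 600 mg per day unless a physician prescribes more, and criterion 35 lets the site investigator exclude someone who cannot comply with the protocol. That depends on judgment, whereas 4.3.4 states a fixed rule.

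**After the edit.** With *or*, the third column becomes admit, exclude, exclude, exclude, which matches 4.3.4 in all four rows. A willing user who completes the washout becomes U no, W no, and is admitted.

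**Calcium anchor.** Criterion 10 counts the week back from baseline; 4.3.4 counts it back from screening. Section 8.1 allows baseline up to 6 weeks after screening, so the two weeks need not coincide. Someone who meets the screening anchor and stays at or below 600 mg/day satisfies both; someone who meets only the baseline anchor does not satisfy 4.3.4. For vitamin D there is no such conflict: 4.3.4 counts back from the start of the protocol, and criterion 9 in 5.2 describes the baseline visit as that start.

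**The case against.** The strongest reply is that nobody would apply the criteria literally. A dose-dependent 8-12 week window has almost no function if willing users need no washout; 4.3.4 states the washout outright; and the change log describes criterion 9 as setting a washout period. Criterion 8, on tanning devices, has the same construction, which suggests a habit of listing two prohibitions in one sentence. Section 4.3.4 is itself protocol text, so 5.2 is not the only rule in force. Criterion 9 also sends sites to the Manual of Operations, which may give the instruction correctly. Much of this stands: the intent is clear, and whether sites lacked a correct instruction cannot be judged from these documents. It does not make the criteria right as written. The parallel with criterion 8 works against the reply as well, because nothing in 4.3.4 contradicts criterion 8, so the list itself gives no sign that 9 and 10 mean something different.

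A second reply is that 4.3.4 admits above-limit users who agree, so willingness is enough. But the agreement there covers a reduction before entry as well as the limit during the study. The unwillingness in criteria 9 and 10 concerns the study period only.

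A reader might also infer that the baseline anchor for calcium undermines the serum calcium eligibility test drawn at screening, and that the week should therefore be counted from screening alone. The documents do not support that.

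- Criterion 31 excludes *high* serum calcium. If above-limit intake affects the test at all, one would expect it to make the test harder to pass.
- Section 6.5 lets a combined screening/baseline visit rely on local blood tests from the previous 6 weeks, so a screening anchor would not guarantee a test taken under the limit.
- The urine calcium-creatinine test for criterion 32 is collected at baseline. A screening-only anchor would remove the control on intake just before it.

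**Conclusion.** The point holds as a minor drafting error. In 5.2 and the synopsis, criteria 9 and 10 are weaker than section 4.3.4 in two of four combinations. The main gap is the willing recent above-limit user with no washout; the unwilling volunteer with no recent above-limit use is partly covered by criterion 35 and section 9.4.

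The conclusion rests on reading the criteria literally and taking 4.3.4 as the intended rule. It does not depend on the Manual: even if the Manual is correct, the protocol text still contradicts itself.

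A reader might infer that ineligible people were enrolled, or that the trial's result is affected. Neither follows. The documents identify no one admitted through this wording and give no basis for estimating a number. Eligibility is settled before a masked 1:1 randomization, and SAP section 2 analyses everyone randomized, so no effect on the primary comparison is claimed. Pre-screening (6.4) and the recording of supplement use at each visit (4.3.4) limit the gap further.

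The two calcium anchors are a small inconsistency to reconcile, with no demonstrated safety consequence.

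**What to change.** Replace *and* with *or* before the unwillingness clause in criteria 9 and 10, in both section 5.2 and the synopsis: 2 criteria × 2 places = 4 one-word edits. Check that the Manual of Operations says the same.

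In the same revision, give the calcium limit one definition in criterion 10 (both places) and in 4.3.4. One suitable form is no more than 600 mg/day from 1 week before screening through the baseline visit. This keeps the stricter start in 4.3.4 and the control on intake before the baseline urine test.

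The cost is editorial. Some willing volunteers will wait 8-12 weeks, but 4.3.4 already requires that, and criterion 34 already allows re-screening once the reason for exclusion has been dealt with. No sample size, endpoint or analysis changes.
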